1.2 Previous similar studies

We could not identify any prior studies comparing the study medications to each other and to placebo. As noted above, azithromycin has been compared to erythromycin and found to cause fewer gastrointestinal side effects in pregnant patients.⁷ Various doses of metronidazole have been compared to each other and the overall rate of GI side effects was found to be low.⁸ Another study of metronidazole compared route of administration (oral v. vaginal) but side effects were not assessed as an outcome.⁹ Gastrointestinal side effects are well-established in doxycycline vs. placebo studies,¹⁰⁻¹² and in the study that compared administration with and without food.³

Regarding the endometrial assessment substudy, a 2014 study that examined bacterial ecology in the vagina, cervix, and uterus did not show a significant change in bacterial species identified by PCR before and after levonorgestrel IUS insertion. Predominant species were genus *Lactobacillus* and *Burkholderia*.⁶ Another study examined bacterial colonization in the endometrium and found a wide variety of bacterial species, even after using a technique designed to minimize contamination from the lower genital tract.¹³ An older study showed mostly negative endometrial cultures at the time of hysterectomy.¹⁴

1.3 Design and Methodology

1.3.1 Research Design and General Methodological Approach

Primary study: We have designed a randomized controlled trial to be conducted at Washington Hospital Center (WHC) and Planned Parenthood of Metropolitan Washington (PPMW) over the course of 6-8 months. A total of 180 English-speaking women will be enrolled with 45 participants in each of the four groups.

The women will be randomized to receive single oral doses of azithromycin 500 mg, doxycycline 200 mg, metronidazole 500 mg, or placebo. Computer-generated randomization will be used to assign participants to one of the four treatment arms. Women receiving placebo will receive antibiotic prophylaxis after completion of the study.

Both the participants and the investigators will be blinded as to the treatment group. This will be accomplished by placing the study medication inside opaque gelatin capsules, a method that has been successful in prior studies.³ We will randomize participants by assigning them to the next of the sequentially numbered sealed opaque study packets, containing the gelatin capsules with study medication inside. A second smaller opaque sealed envelope will also be inside the study packet. This envelope will be opened after completion of all study procedure and will only say if the participant received placebo, so that additional antibiotics can be given.

Participants will swallow the appropriate medication approximately 30-60 minutes prior to the surgical abortion. We will assess side effects via written questionnaire immediately before the start of the procedure and in the recovery room. Study population will be all eligible patients undergoing surgical abortion in the first trimester at PPMW and at WHC.

For the substudy 40 women will be recruited to undergo immediate post-procedure endometrial sampling using a suction-piston device. Due to the double-blind nature of this study, enrollment into the substudy will not be by group. Thus there are likely to be unequal group sizes. For a pilot substudy such as this, unequal numbers within groups will not detract from the utility of the results.

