1.3.3 Participant recruitment and allocation

The research coordinator, co-investigators, or other designated individual will recruit women to the study. WHC and PPMW serve representative samples of the Washington metropolitan area. Baseline characteristics of the outpatient center at WHC and at PPMW in 2012 are shown below:

Age (years)	WHC	PPMW
<20	4%	12%
20-24	11%	38%
25-29	11%	25%
30-39	68%	21%
40 or more	6%	5%
Race		
Black, non-Hispanic	22%	65%
White, non-Hispanic	61%	16%
Hispanic	11%	8%
Multiracial	0%	8%
Other/unknown	6%	3%

WHC patients are generally referred from their general obstetrician's office for abortion and are seen in the private outpatient office. We will recruit eligible patients on days when we are not recruiting at PPMW.

PPMW has a diverse patient population, with a majority of women being African American and age 20-

29 years old. We will recruit from the PPMW clinic in Washington DC on Wednesdays and Thursdays. If needed to meet the recruitment timeline, we can expand recruitment to the PPMW clinic in Silver Spring, Maryland, on Fridays.

The potential participant will be approached for study recruitment only after she has signed informed consent for the first-trimester surgical abortion. She will be approached by a research staff member or co-investigator and asked to participate in the study. A detailed explanation of the study will be provided and written informed consent will be obtained (Appendix A). The patient will be given a copy of her signed informed consent. After the consent is signed, eligibility for the study will be confirmed.

For randomization, a Medstar Research Institute statistician not involved in the conduct of the study will produce the allocation sequence using a computer generating pseudo-random sequence. The Medstar Research Pharmacy will prepare sequentially numbered sealed opaque allocation packets containing the appropriate study drugs placed within opaque gelatin capsules. The packets will not be assigned to a participant until eligibility is confirmed. To preserve blinding while allowing participants receiving placebo to be given antibiotics after study completion, a small sealed opaque envelope will be placed inside the packet with the gelatin capsules. The envelope will contain a folded piece of paper saying only "Placebo" or "Not placebo."

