1.3.5 Admission Procedure

After informed consent has been obtained and eligibility confirmed, the participant will complete a baseline survey of demographic, medical history, and baseline symptoms, notably nausea (Appendix C). If the participant is interested in the substudy, a second consent will be signed for the substudy. She will then be assigned the next of the sequentially numbered randomization packet. At the time of pre-medication with ibuprofen and other standard medications, the participant will take the study drug from the first envelope with water approximately 30-60 minutes prior to procedure (15-90 minutes acceptable range). Time of administration will be recorded on the patient's chart. All other medications given concurrently will be recorded. At PPMW and WHC, patients are typically given ibuprofen 800 mg, tramadol 50 mg, alprazolam 0.25 mg, and promethazine 25 mg. While we plan to use this for all study participants, medications will be tailored to the need of each woman, such as, for example, allergies to medications.

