1.3.11 Number of Subjects and Statistical Power

Sample size: 180 women for main study

To detect a 30% difference in a given outcome compared to the placebo group, we will need to enroll 45 women per group to achieve a power of 80% with alpha of 0.05.

For the endometrial sampling substudy, we will enroll 40 women. As this has not been done previously,

we cannot predict results with any accuracy. We expect that roughly 10 women per group will give us enough data to understand if this methodology will be fruitful for future research, without undue risk to a large number of women at this early stage. Enrollment in the sub-study may be more challenging but we need many fewer participants. To give a rough idea of power, the substudy will have 85% power with alpha of 0.05 to detect a reduction in positive culture (any bacteria detected) from 90% with placebo to 20% in a treatment group. This assumes 10 women per group.

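### Blinding does not force unequal substudy arms: substudy consent precedes packet assignment, so it could be a randomisation stratum, yet the 10 women per group behind the substudy power is left to chance

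*Combined protocol and SAP*

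**What the plan says.** Section 1.3.1 recruits 40 women to the substudy and explains the lack of balance in arm sizes: "Due to the double-blind nature of this study, enrollment into the substudy will not be by group. Thus there are likely to be unequal group". It then accepts the consequence: "For a pilot substudy such as this, unequal numbers within groups will not detract from the utility of the results".

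Section 1.3.5 gives the order of events at admission: "If the participant is interested in the substudy, a second consent will be signed for the substudy", and after that, "She will then be assigned the next of the sequentially numbered randomization packet".

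Section 1.3.3 places sequence and packets away from the clinic: "a Medstar Research Institute statistician not involved in the conduct of the study will produce the allocation sequence using a computer generating pseudo-random sequence", and "The Medstar Research Pharmacy will prepare sequentially numbered sealed opaque allocation packets containing the appropriate study drugs placed within opaque gelatin capsules". No blocking, and no stratification by substudy status, is described. The same section puts a slip in each packet showing only whether the woman had placebo; site staff open it after her final questionnaire.

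Section 1.3.11 expects roughly 10 women per group and gives 85% power at alpha 0.05 for 90% versus 20% positive cultures, adding: "This assumes 10 women per group".

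**The concern.** The plan treats imbalance as a price of blinding. Blinded staff cannot pick women by arm, but balance does not require them to. A woman's substudy status is known before she is allocated, and the people who make the list and fill the packets are outside the blind. They could hold a separate balanced series for substudy women, and the site would need to know only which series to draw from.

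Without that, the arm sizes are a chance draw, while the power statement rests on 10 in each. Every drug-placebo contrast shares one placebo group. Section 1.7 says that differences from placebo will help to show whether the method merits a larger study. A badly short arm would weaken that reading, in women who have already had the extra sampling.

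**Working it through.** **Inputs.** 40 samples, four arms (1.3.1, 1.3.2); 45 per arm in the main trial (1.3.1); p1 = 0.90, p2 = 0.20, alpha 0.05, 10 per group, 85% (1.3.11). Sidedness is not stated; two-sided is assumed because it reproduces 85% (one-sided gives 93%).

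**The plan's figure.** Normal approximation with continuity correction:

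Power = Φ{[(p1 − p2) − c − 1.96·SE0] / SE1}, where c = ½(1/n1 + 1/n2), SE0 = √[p̄(1 − p̄)(1/n1 + 1/n2)] and SE1 = √[p1(1 − p1)/n1 + p2(1 − p2)/n2].

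At 10 versus 10: p̄ = 0.55, c = 0.10, SE0 = 0.2225, SE1 = 0.1581. Power = Φ[(0.70 − 0.10 − 0.436)/0.1581] = Φ(1.037) = 0.850. The stated 85% reproduces. Two-sided Fisher exact power is 0.841.

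**Spread of arm sizes.**
- Simple randomisation: SD = √(40 × ¼ × ¾) = 2.74.
- 40 drawn at random from 45 per arm: 2.74 × √(140/179) = 2.42.
- 40 drawn from one block of 48 (12 per arm): 2.74 × √(8/47) = 1.13.

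**Consequences.** Arm sizes were simulated from these three distributions and power was evaluated at each draw.

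| | Simple randomisation | 40 from 45 per arm | 40 from one block of 48 |
|---|---|---|---|
| Exactly 10 in all four arms | 0.4% | 0.6% | 5% |
| At least one arm with 7 or fewer | 64% | 55% | 7% |
| Mean power, plan's formula | 80% | 81% | 84% |
| Mean power, Fisher exact | 87% | 88% | 88% |
| At least one of three placebo contrasts below 80%, Fisher | 27% | 19% | under 1% |

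Mean Fisher power is not below its 10-versus-10 value because the exact test is discrete, and 10 versus 10 happens to be a conservative point.

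**Deducible packets.** Suppose staff know the block structure and see every earlier slip. In a block with k placebo and m other packets, the expected number whose placebo status is known in advance is m/(k + 1) + k/(m + 1).
- Block of 4 (k = 1, m = 3): 1.50 + 0.25 = 1.75 of 4, about 44%.
- Block of 48 (k = 12, m = 36): 2.77 + 0.32 = 3.09 of 48, about 6%. This counts the block as run to its end.

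**Allocated is not sampled.** Sections 1.3.2 and 1.3.7 allow exclusion after the packet is assigned, at a rate not given. At an assumed 2%, 5% or 10%, the chance that all of the first 40 women yield a sample is 0.98^40 = 0.45, 0.95^40 = 0.13 or 0.90^40 = 0.01. The arms would therefore be close to 10 rather than exactly 10. The block-of-48 column treats the 40 samples as a random 40 of the 48.

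**The case against.** The plan discloses the imbalance and judges it harmless. The substudy is a feasibility pilot, section 1.3.11 offers its power only as a rough idea, and no guarantee of 10 per arm was given. All of that stands and keeps the severity low. It does not make blinding the reason for the imbalance.

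A reader might infer a serious loss of power from the Fisher values of 65% at 7 versus 7 and 44% at 6 versus 6. The design does not support that. The total is fixed at 40, so a small arm is usually offset by larger ones. Placebo and some drug arm are both at 7 or fewer in only 2.5% to 4.4% of trials, and 7 placebo versus 11 drug still gives 87%. Per contrast, Fisher power is below 80% in 8% to 11% of trials. The 80% line is a convention used here, not a criterion in the plan.

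A reader might also infer that a blocked series carries no risk to the blind. That fails, because site staff open a placebo slip after each woman. In a short blocked series those slips reveal later packets, and these women also count in the main trial, whose outcomes are self-reported. This is the strongest objection. It rules out small fixed blocks but not one large concealed block.

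Nor would balance rescue the hypothesis in section 1.1.2 that metronidazole leaves aerobic bacteria undiminished. The 90% versus 20% calculation does not address a claim of no decrease, even at 10 per arm.

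**Conclusion.** The point holds in a limited form. The order of events in section 1.3.5 means that blinding does not require unequal substudy arms, and sections 1.3.1 and 1.3.11 do not fit together: the split assumed for 85% power occurs in under 1% of trials. By the plan's own formula, average power is about 80% to 81%, a loss of 4 to 5 points; by Fisher's test the average is not reduced. What balance chiefly buys is protection against a badly short arm.

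This rests on a two-sided test and on substudy women being in effect a random draw from the main sequence. If that sequence is in fact blocked and substudy women enter nearly consecutively, the arms would vary less than shown. The plan does not describe this.

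**What to change.** Before enrolment, replace the blinding sentence in section 1.3.1 with, for example: *Randomisation is stratified by signed substudy consent. Women who have signed it receive the next packet from a separate sealed series, prepared by the same statistician and pharmacy as a single randomly ordered block of 48 (12 per arm). Its composition is not disclosed to the sites.* Large blocks of randomly varied size would also serve; small fixed blocks would not. State that women excluded after allocation are replaced from the same series, and that arms will be near 10, not exactly 10.

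Costs:
- A second list and a second packet series, shared across the sites. Section 1.3.3 recruits at the hospital on days without recruitment at the other site, so one series can be moved between them.
- Up to 8 unused packets if 40 women suffice. The budget in section 3.2 covers 50 doses of each drug and 400 capsules, which at two per dose is 200 packets, so unused ones come out of that supply.
- A small residual predictability, about 6% at most if the block structure became known.

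No extra participants or procedures are needed.

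If the second series is not adopted, delete blinding as the justification and restate the section 1.3.11 power as about 80% on average over random arm sizes by the same formula.

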1.3.2 Criteria for selection of participants

We will enroll up to 200 women so that 180 women complete the final post-procedure questionnaire. We will enroll women who meet the following criteria (see Appendix H):

- Women in good general health
- Age 18 or over
- Seeking non-urgent surgical termination of pregnancy
- Gestational age of 5 0/7 to 13 6/7 weeks, confirmed by sonography
- English-speaking

Women who meet any of the following criteria will be excluded:

- Early pregnancy failure or fetal demise
- Intolerance, allergy, or contraindication to any of the study medications
- Inability to tolerate oral intake due to current nausea or vomiting
- Desire to use intravenous sedation.

For the substudy, women will be recruited until 40 samples have been obtained. The only inclusion criterion is eligibility for the main study. We will exclude women from the substudy if procedural complications such as perforation or hemorrhage occur that would make endometrial sampling unsafe or inadvisable.

1.3.3 Participant recruitment and allocation

The research coordinator, co-investigators, or other designated individual will recruit women to the study. WHC and PPMW serve representative samples of the Washington metropolitan area. Baseline characteristics of the outpatient center at WHC and at PPMW in 2012 are shown below:

Age (years)	WHC	PPMW
<20	4%	12%
20-24	11%	38%
25-29	11%	25%
30-39	68%	21%
40 or more	6%	5%
Race		
Black, non-Hispanic	22%	65%
White, non-Hispanic	61%	16%
Hispanic	11%	8%
Multiracial	0%	8%
Other/unknown	6%	3%

WHC patients are generally referred from their general obstetrician's office for abortion and are seen in the private outpatient office. We will recruit eligible patients on days when we are not recruiting at PPMW.

PPMW has a diverse patient population, with a majority of women being African American and age 20-

29 years old. We will recruit from the PPMW clinic in Washington DC on Wednesdays and Thursdays. If needed to meet the recruitment timeline, we can expand recruitment to the PPMW clinic in Silver Spring, Maryland, on Fridays.

The potential participant will be approached for study recruitment only after she has signed informed consent for the first-trimester surgical abortion. She will be approached by a research staff member or co-investigator and asked to participate in the study. A detailed explanation of the study will be provided and written informed consent will be obtained (Appendix A). The patient will be given a copy of her signed informed consent. After the consent is signed, eligibility for the study will be confirmed.

For randomization, a Medstar Research Institute statistician not involved in the conduct of the study will produce the allocation sequence using a computer generating pseudo-random sequence. The Medstar Research Pharmacy will prepare sequentially numbered sealed opaque allocation packets containing the appropriate study drugs placed within opaque gelatin capsules. The packets will not be assigned to a participant until eligibility is confirmed. To preserve blinding while allowing participants receiving placebo to be given antibiotics after study completion, a small sealed opaque envelope will be placed inside the packet with the gelatin capsules. The envelope will contain a folded piece of paper saying only "Placebo" or "Not placebo."

The patient will only open the randomization packet at take the study medication at the time of pre-medication for her abortion procedure. She will hand the small envelope to the research staff. The allocation number will be recorded twice on the participant's chart. At the time of allocation, the small envelope will be attached to the participant's chart, and will be opened by the PPMW or WHC staff after collection of the final post-procedure questionnaire. If the participant is in the placebo group, appropriate post-procedure antibiotics will be given, such as azithromycin 1 g or doxycycline 100 mg twice daily for 3 days.

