3.1 Line-Item Budget

3.2 Budget Justification

A. Personnel

[name] will lead the study. She will be responsible for subject recruitment, assist in data analysis, and dissemination of findings. [name] will assist in data collection, data analysis and dissemination of findings. WHC and PPMW physicians will perform procedures for the study participants. The research coordinator, [name] will assist in subject recruitment, obtaining consent, treatment allocation and concealment. Budget will include salary support for the research coordinator.

For the substudy, only study investigators ([name], [name], [name], [name]) will obtain the pipelle samples.

Biostatistics support will be obtained through the research department at Washington MedStar Hospital, as needed.

B. Equipment

No additional equipment will be needed for the study.

C. Materials and Supplies

Biostatistics support: \$100/hour x 10 hours = \$1000

Pharmacy costs

Study drugs:

Azithromycin 250 mg x 100

Doxycycline 100 mg x 100

Metronidazole 250 mg x 100

Gelatin capsules x 400

Endometrial pipelles x 50

Culture media, 50 aerobic and 50 anaerobic.

Lab services at University of Pittsburgh

Shipping

Venipuncture supplies

Lab services for serum antibiotic testing

Shipping

Office supplies/copies

D. Participant Costs

180 participants will receive a \$50 gift card for participation on the day of their procedure (\$9,000). The 40 substudy participants will receive an additional \$50 gift card (\$2,000).

E. Travel

Travel will occur between the two sites of the study, WHC and PPMW, for both the research coordinator and the co-investigator. Estimated travel expenses are based on cost of mass transit and/or driving costs.

F. Other Costs

These costs will include copying and printing of consent and questionnaire forms, and the cost of materials and shipping.

Consultant Services

Medstar Washington Hospital biostatistician services will be obtained.

Contractual Costs

PPMW will receive \$50 per study participant to cover costs incurred with study participation.

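### The allocation plan states no restriction and no stratification by clinic; concealed, randomly varied blocks within each clinic, with site in the analysis, would be a cheap improvement.

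*Combined protocol and SAP*

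**What the plan says.** Section 1.3.1 sets the target: "A total of 180 English-speaking women will be enrolled with 45 participants in each of the four groups". Section 1.3.2 adds the ceiling: "We will enroll up to 200 women so that 180 women complete the final post-procedure questionnaire".

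The method is given in three places. Section 1.3.1 says "Computer-generated randomization will be used to assign participants to one of the four treatment arms", and that this is done by "assigning them to the next of the sequentially numbered sealed opaque study packets". Section 1.3.3 says that a statistician outside the study "will produce the allocation sequence using a computer generating pseudo-random sequence", and that the research pharmacy prepares the packets. Restriction, strata and a separate series per clinic are not mentioned. Section 1.3.10 leaves the choice between parametric and non-parametric methods open and does not mention site.

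Each packet also holds a slip showing whether the woman had placebo. It "will be opened by the PPMW or WHC staff after collection of the final post-procedure questionnaire".

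The budget in section 3.2 lists "Azithromycin 250 mg x 100", and likewise 100 half-dose units of each of the other two drugs, plus 400 capsules.

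**The concern.** Two clinics feed one four-arm trial, and the 2012 table in section 1.3.3 shows how unlike they are. Age 30-39 is 68% at WHC and 21% at PPMW; Black non-Hispanic is 22% and 65%. WHC patients are generally referred from an obstetrician's office, and section 1.3.6 leaves the procedure to each facility's usual practice. The outcomes are largely self-reported. If clinic is spread unevenly over the arms, patient mix and local practice are spread unevenly too, and no planned analysis would take account of it. The stated target of 45 per arm also has no stated mechanism behind it.

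The standard remedy, blocking, has a trap in this trial. Because placebo status is revealed after each woman, small fixed blocks could let staff work out later packets.

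**Working it through.** **1. The plan's own 45 per group.** Section 1.3.11 gives 45 per group for 80% power at alpha 0.05 "To detect a 30% difference in a given outcome compared to the placebo group". It states neither a baseline rate nor whether the 30% is absolute. Taking two-sided alpha and an absolute difference, with placebo rates of 5-60%, the usual two-proportion formula gives 27-43 per group, or 34-49 with continuity correction. It gives exactly 45 at 20% vs 50% with the correction. The figure reproduces.

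**2. Arm sizes under the two readings** (180 allocated)

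| Reading | SD of one arm | 95% range | Expected smallest arm |
|---|---|---|---|
| Simple 1:1:1:1 | √(180 × 0.25 × 0.75) = 5.8 | 34-57 | 38 |
| List of 50 per arm, first 180 used | 1.8 | 41-48 | 43 |

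The list comes from the budget: 100 × 250 mg / 500 mg = 50 courses per drug, and 400 capsules / 2 = 200 packets. It keeps the arms close to 45 but does not fix them there.

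**3. WHC share.** Section 1.3.13 expects 2-6 women a week at WHC out of 10-15 overall: 2/10 = 20% and 6/15 = 40%.

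**4. Site balance without strata.** Take 45 per arm and let WHC share be p, so the WHC count in each arm is binomial(45, p). The SD of the difference in site share between two arms is √(2p(1−p)/45). Fifteen points of 45 is 6.75 women, so the event is a difference of 7 or more.

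| p | SD of difference | One drug vs placebo ≥15 points | At least one of three drugs vs placebo |
|---|---|---|---|
| 20% | 8.4 points | 9% | 21% |
| 30% | 9.7 points | 13% | 31% |
| 40% | 10.3 points | 16% | 36% |

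Letting arm sizes vary, by simple allocation or by the list in step 2, gives about 8-15% and 19-34%. Equal totals alone therefore do almost nothing for site balance.

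**5. What it costs**
- Power against placebo, averaged over simple allocation: 82.1% instead of 82.8% at 30% vs 60% (5th percentile 76.9%), and 85.4% instead of 86.0% at 20% vs 50% (5th percentile 80.5%).
- Shift in an estimate: if outcome rates differed by 20 points between clinics (an assumption), a 15-point site imbalance would move a between-arm difference by 0.15 × 20 = 3 points, against the 30-point target.

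**6. Blocks of 8 and 12, varied at random, within clinic.** In each clinic only the last block can be part-used, and it holds at most 12/4 = 3 of any arm. WHC counts can then differ between two arms by at most 3 women, about 3/45 = 7 points, so a 15-point imbalance cannot arise by allocation. Simulated arm sizes at 180 were 42-48.

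**7. Predictability once placebo status is revealed.** In a block of B with k = B/4 placebos, a packet's placebo status is certain in advance if all placebos have been used, or if only placebos remain. The expected share is [(B−k)/(k+1) + k/(B−k+1)]/B:
- B = 4: (1.5 + 0.25)/4 = 44%
- B = 8: (2 + 0.286)/8 = 29%
- B = 12: (2.25 + 0.3)/12 = 21%

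These figures assume that staff know the block boundaries and see each slip before the next allocation.

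**The case against.** The strongest reply is that silence is not a method. A permuted-block list is also a computer-generated pseudo-random sequence, so the statistician may already intend restriction, and the order of 50 courses per drug points that way. This stands, and it rules out three stronger readings.
- A reader might infer that simple randomisation is used and the arms will miss 45 badly. The text does not say so, and exact equality is a poor benchmark: the recommended blocks do not guarantee it either.
- A reader might infer that a drug could run out. The pharmacy fills packets from the list, so any excess would show at preparation. Fifty courses also match one quarter of the 200 ceiling.
- A reader might infer a real loss of power. The average loss is under 1 point even in the worse case.

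It is also fair to say that the documents do not show that clinic predicts nausea, vomiting or satisfaction. Routine pre-medication is described identically for both clinics, and intravenous sedation is excluded. Chance imbalance under valid randomisation does not bias the estimate. Concealment is well described, and the protocol never proposes blocks of 4, so step 7 is a caution about the repair and not a defect in the plan.

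One thing is not answered: an equal-total list leaves site balance to chance, and section 1.3.10 does not adjust for it. The unequal group sizes accepted in section 1.3.1 concern only the 40-woman substudy.

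**Conclusion.** The point holds as a cheap improvement, not as a threat to validity. The plan states no restriction, no stratification by clinic and no site adjustment. The chance that at least one drug arm is 15 or more points from placebo in site share is about 20-36%, or about 8-16% for one comparison. This rests on a WHC share of 20-40%, inferred from the recruitment estimates, and on about 45 women per arm. What is gained is precision, balance and credibility. If the statistician already intends an equal-total list, the gain is almost entirely in site balance, because arm sizes would be near 45 anyway.

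**What to change.** In section 1.3.3, state that the statistician generates a separate permuted-block sequence for each clinic. Each clinic has its own numbered packet series, with block sizes varied at random (for example 8 and 12) and known only to the statistician and pharmacy. Rule out small fixed blocks, and say why. If the optional Silver Spring clinic opens, treat it as a further stratum with its own series. In section 1.3.10, include site in the between-arm comparison.

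The cost is a change in the randomisation program and two labelled packet series from the same pharmacy. A few blocks will be part-used, the arms will be near-equal rather than exactly equal, and a small degree of predictability remains. The change has to be made before packets are filled; site adjustment can still be added before unblinding.
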